2.0	[REDACTED]	
1. Section 2.2: Number (n, %) of subjects and eyes with contact lens related (i.e., related and possibly related) serious and significant ocular adverse events (AEs), including best corrected logMAR loss > 0.20 logMAR (10 letters)..
 
2. Section 3.1: Clarified the refractive error for anticipated study population to be best sphere refraction for level of myopia.
 
3. Section 7: Added logMAR BCVA assessment at baseline and during each study visit.
 
4. Section 6.2 and 7: Updated the chart number for high contrast near logMAR VA to be 2106C.
 
5. Unscheduled visit procedures were updated to allow over-refraction, lens modification, and the logMAR VA with spherocylindrical correction.
 
6. Primary safety endpoint added to section 14.5, "Primary Analysis."
 
7. Section 7: Clarified that general health questionnaire would also be completed during PRO follow-up.
 
8. Attached lens power modification guide for all 3 test lenses. The run-in lens modification is already described within the study procedures.
 
9. Added assigned lens codes to section 6 to connect the lens design with the
		07OCT2021
-----	------------	--	--	-----------

Clinical Study Protocol
Johnson & Johnson Vision Care, Inc.

Version	Originator	Description of Change(s) and Section Number(s) Affected	Justification for Change	Date
		appropriate power modification instructions.		
3.0	[REDACTED]	1. Section 7: Moved logMAR VA with spherocylindrical correction procedure from the exit evaluation to end of V5. 2. Section 14: Included reference to standalone SAP which will be developed and finalized prior to database lock.		10/19/2021
4.0	[REDACTED]	1. Updated the designated Clinical Operations Manager on the signature page due to a personnel change. 2. Corrected the primary safety endpoint in the Synopsis and Section 2.2 to read 'best corrected logMAR loss ≥ 0.20 logMAR,' not '> 0.20 logMAR.' 3. Removed 'Treatment 2,' a typo, from the header of visit 5 in Table 3, Section 7.1.	1-3: Administrative changes to ensure the accuracy of the protocol and clarify roles/responsibilities.	29MAR2022

SYNOPSIS

Protocol Title	Visual Performance of Soft Contact Lenses with Myopia Control Optics
Sponsor	JJVC, [name]
Clinical Phase	Clinical trial phase: Confirmatory* Design control phase: 
 • EMO-118: Phase 3 • EMO-114: Phase 0 
*This is a research study but will be assigned the confirmatory clinical trial phase due to the advanced development stage of the EMO-118 investigational product.

Clinical Study Protocol
Johnson & Johnson Vision Care, Inc.

Trial Registration	This study will be registered on ClinicalTrials.gov by the sponsor because this study is in the confirmatory clinical trial phase.
Test Article(s)	
Investigational Products:
 
Daily disposable soft contact lenses (SCL) made in senofilcon A material with the same parameters but differing optical designs
 
 • EMO-118 (Test 1) • EMO-114 (Test 2) 
Approved Products:
 
 • MiSight® 1 day, a SCL made in omafilcon A material approved by the US-FDA for slowing the progression of myopia in children (Control) • 1-Day Acuvue® Moist Brand Contact Lenses manufactured in etafilcon A material (Run-in period)
Wear and Replacement Schedules	
Wear Schedule: Daily wear
 
Replacement Schedule: Daily disposable

Objectives	
Primary Objective
 
The primary objective is to evaluate the logMAR visual performance of soft contact lenses featuring myopia control optical designs.
 
Exploratory Objectives
 
The exploratory objectives of the study are to assess:
 
 • logMAR visual performance at 4 m under varying luminance and contrast conditions • logMAR visual performance at 40 cm under high and low contrast conditions • Patient-reported outcomes at fitting and follow-up • Assess safety through adverse events, slit lamp findings, and subject-reported ocular symptoms • Number of power modifications and over-refraction with first trial lens at fitting • Over-refraction at follow-up • Lens fitting characteristics
Study Endpoints	
Primary endpoint(s):
 
 • Binocular distance (4 m) high luminance high contrast (HLHC) logMAR visual acuity, measured per [REDACTED]

Clinical Study Protocol
Johnson & Johnson Vision Care, Inc.

	
Primary safety endpoint:
 
 • Number (n, %) of subjects and eyes with contact lens related (i.e., related and possibly related) serious and significant ocular adverse events (AEs), including best corrected logMAR loss ≥ 0.20 logMAR (10 letters). 
Other exploratory endpoints:
 
 • Monocular HLHC logMAR visual acuity at 4 m • Binocular high luminance low contrast (HLLC) logMAR visual acuity at 4 m • Monocular HLLC logMAR visual acuity at 4 m • Binocular low luminance high contrast (LLHC) logMAR visual acuity at 4 m • Monocular LLHC logMAR visual acuity at 4 m • Binocular HLHC logMAR visual acuity at 40 cm • Binocular HLLC logMAR visual acuity at 40 cm • Subjective vision, comfort, and ease of handling • Non-significant AEs and non-ocular AEs • Slit lamp findings per the ISO 11980 grading scale • Subject-reported ocular symptoms • Number of contact lens insertion attempts per eye at fitting • Subjective best sphere over-refraction with the first trial lens • Subjective best sphere over-refraction at follow-up • Number of power modifications at fitting • Lens fitting characteristics
Study Design	
This is a multi-site, bilateral, dispensing, randomized, controlled, single-masked, 3x3 crossover study with a run-in period. Following the run-in period, each subject will be bilaterally fitted with one of the three study contact lenses test articles in each of the three periods.
 
There will be a total of 5 planned visits:
 
Visit 1: Screening, baseline evaluation, run-in lens fit and application/removal training
 
Visit 2: Run-in follow-up and treatment #1 fit
 
Visit 3: Treatment #1 follow-up and Treatment #2 fit
 
Visit 4: Treatment #2 follow-up and Treatment #3 fit
 
Visit 5: Treatment #3 follow-up and study exit

Clinical Study Protocol
Johnson & Johnson Vision Care, Inc.

	See the flow chart at the end of the synopsis table for the schematic of the study visits and procedures of main observations (Figure 1).
Sample Size	The goal is to enroll approximately 75 eligible subjects and complete 50. Up to 6 sites are expected to enroll approximately 15 subjects each.
Study Duration	There will be 5 visits in total per subject (not including application and removal training). Total study duration including the enrollment period is expected to be approximately 4 months, with an expected enrollment period of 2 months.
Anticipated Study Population	Healthy male and female subjects between 7 and 17 years old with best sphere refraction from -1.00 to -4.50 D (inclusive) and 0.75 D or less astigmatism will be recruited. The goal is to have the number of 7-12 year old subjects approximately equal to the number of 13-17 year old subjects. Potential subjects can be spectacle lens wearers, current soft lens wearers, or symptomatic myopes (e.g., with complaints of blurry vision) currently without correction. There are no restrictions regarding race/ethnicity of the subjects.
Eligibility Criteria - Inclusion	
Potential subjects must satisfy all of the following criteria to be enrolled in the study:
 
Inclusion Criteria following Screening
 
The subject must:
 
 1. Read (or be read to) and sign the CHILDREN'S ASSENT (Information and Assent Form) and receive a fully executed copy of the form. 2. Have parents or legal guardians who must read, understand, and sign the STATEMENT OF INFORMED CONSENT (Parental Permission Form and Authorization to Use and Disclose Medical Information). 3. Appear able and willing to adhere to the instructions set forth in this clinical protocol. 4. Be between 7 and 17 (inclusive) years of age at the time of screening. 5. By self-report, habitually wear soft contact lenses or be a current non-contact lens wearer interested in soft lens wear. 
Inclusion Criteria following Baseline Evaluation

Clinical Study Protocol
Johnson & Johnson Vision Care, Inc.

	
 6. The non-vertex corrected best sphere distance refraction must be between -1.00 D and -4.50 D (inclusive) in each eye. 7. The magnitude of the cylindrical component of the subject's vertex-corrected distance refraction must be less than or equal to 0.75 D (inclusive) in each eye with any degree of axis. 8. The distance visual acuity with best sphere distance correction must be 20/25 or better in each eye. 9. Have \leq 1.50 D difference in subjective best-sphere refraction between the two eyes. 10. Have 20/40 or better vision in each eye with wearable spectacles or uncorrected.
Eligibility Criteria – Exclusion	
Potential subjects who meet any of the following criteria will be excluded from participating in the study:
 
Exclusion Criteria following Screening
 
The subject must not:
 
 1. Be currently pregnant or lactating. 2. Be diabetic. 3. Be currently using any ocular medications. Lubricants (artificial tears) eyedrops are allowed. 4. Have any current ocular infection of any type. 5. Have any systemic disease (e.g., Sjogren's Syndrome), allergies, infectious disease (e.g., hepatitis, tuberculosis), contagious immunosuppressive diseases (e.g., HIV), autoimmune disease (e.g., rheumatoid arthritis), any underlying medical condition that makes subjects at risk of severe COVID complications, a history of serious mental illness or seizures, or other diseases, by parent or legal guardian's self-report, which are known to interfere with contact lens wear and/or participation in the study. 6. Use of systemic medication (e.g., chronic steroid use) that are known to interfere with contact lens wear and/or participation in the study. See section 9.1 for additional details regarding excluded systemic medications. 7. Have habitually worn rigid gas permeable (RGP) lenses, orthokeratology lenses, or hybrid lenses (e.g. SynergEyes, SoftPerm) within the past 30 days. 8. Be currently wearing lenses in an extended wear modality.

Clinical Study Protocol
Johnson & Johnson Vision Care, Inc.

	
9. Be currently wearing soft contact lenses for astigmatism in either eye.
 
10. Have participated in a contact lens or lens care product clinical trial within 7 days prior to study enrollment.
 
11. Be an employee (e.g., Investigator, Coordinator, Technician) or immediate family member of an employee (including partner, child, parent, grandparent, grandchild or sibling of the employee or their spouse) of the clinical site.
 
12. Children who are wards of the State or any other agency, institution, or entity.
 
Exclusion Criteria following Baseline Evaluation
 
The subject must not:
 
13. Have any ocular allergies, infections, or other ocular abnormalities that are known to interfere with contact lens wear and/or participation in the study. This may include, but is not limited to, entropion, ectropion, chalazia, recurrent styes, glaucoma, history of recurrent corneal erosions, aphakia, moderate or above corneal distortion, herpetic keratitis.
 
14. Have grade 3 or greater palpebral conjunctival observations or any other grade 2 slit lamp findings on the ISO 11980 classification scale.
 
15. Have strabismus (intermittent or constant) or amblyopia.
 
16. Have a history or signs of a contact lens-related corneal inflammatory event (e.g., past peripheral ulcer or round peripheral scar).
 
17. Have any central corneal scar.
 
18. Have a pupil diameter under bright illumination of less than 2 mm in either eye.

Disallowed Medications/Interventions	See section 9.1 for details regarding disallowed systemic medications.
Measurements and Procedures	Primary endpoint: logMAR Visual Acuity at distance (4 m)
Microbiology or Other Laboratory Testing	None

[figure not shown]
Clinical Study Protocol
Johnson & Johnson Vision Care, Inc.

Study Termination	
The occurrence of an Unanticipated Adverse Device Effect (UADE) or Serious Adverse Event (SAE) for which a causal relationship to a test article cannot be ruled out, will result in stopping further dispensing investigational product. In the event of a UADE or SAE, the Sponsor Medical Monitor may unmask the treatment regimen of subject(s) and may discuss this with the Principal Investigator before any further subjects are enrolled.
 
See section 11 for additional study-specific stopping rules.

Ancillary Supplies/ Study-Specific Materials	
The following supplies may be provided to the clinical sites as needed:
 
• Lens cases• Fluorescein strips (either 0.6 mg or 1.0 mg)• Precision Vision distance (4 m) high and low contrast ETDRS logMAR visual acuity charts• Precision Vision near (40 cm) high and low contrast ETDRS logMAR visual acuity charts• Precision Vision LED Illuminator Cabinet• Precision Vision large mesopic filter for ETDRS Illuminator Cabinet• Sekonic light meter
Principal Investigator(s) and Study Institution(s)/Site(s)	A full list of Principal Investigators, clinical sites, and institutions is kept separately from the Study Protocol and is included in the study Trial Master File.

Clinical Study Protocol

Johnson & Johnson Vision Care, Inc.

Figure 1: Study Flowchart

Clinical Study Protocol

Johnson & Johnson Vision Care, Inc.

COMMONLY USED ABBREVIATIONS, ACRONYMS AND DEFINITIONS OF TERMS

ADE	Adverse Device Effect
ADHD	Attention Deficit Hyperactivity Disorder
AE	Adverse Event/Adverse Experience
BSCVA	Best Spectacle Corrected Visual Acuity
CFR	Code of Federal Regulations
CLUE	Contact Lens User Experience
COM	Clinical Operations Manager
COVID-19	Coronavirus Disease 2019
CRA	Clinical Research Associate
CRF	Case Report Form
CRO	Contract Research Organization
████████	████████
D	Diopter
DMC	Data Monitoring Committee
eCRF	Electronic Case Report Form
EDC	Electronic Data Capture
ETDRS	Early Treatment Diabetic Retinopathy Study
FDA	Food and Drug Administration
GCP	Good Clinical Practice
HIPAA	Health Insurance Portability and Accountability Act
HIV	Human Immunodeficiency Virus
IB	Investigator's Brochure
ICH	International Council for Harmonization
IDE	Investigational Device Exemption
IEC	Independent Ethics Committee
IRB	Institutional Review Board
ISO	International Organization for Standardization
ITT	Intent-to-Treat
JJVC	Johnson & Johnson Vision Care, Inc.
LASIK	Laser-Assisted in Situ Keratomileusis
LogMAR	Logarithm of Minimal Angle of Resolution
OD	Right Eye
OS	Left Eye
OU	Both Eyes
PIG	Patient Instruction Guide
PQC	Product Quality Complaint
PRK	Photorefractive Keratectomy
PRO	Patient Reported Outcome
QA	Quality Assurance
SAE	Serious Adverse Event/Serious Adverse Experience
SAP	Statistical Analysis Plan
SAS	Statistical Analysis System
SD	Standard Deviation

Clinical Study Protocol
Johnson & Johnson Vision Care, Inc.

UADE
USADE
VA

Unanticipated Adverse Device Effect
Unanticipated Serious Adverse Device Effect
Visual Acuity

Clinical Study Protocol

Johnson & Johnson Vision Care, Inc.

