11. STUDY TERMINATION

The occurrence of one or more Unanticipated Serious Adverse Device Effect (USADE), or any SAE where the relationship to study agent cannot be ruled out, may result in stopping

Clinical Study Protocol

Johnson & Johnson Vision Care, Inc.

further dispensing of test article. In the event of a USADE or SAE, the Sponsor may unmask the treatment regimen for the subject(s) and will discuss this with the Investigator before any further subjects are enrolled.

The Sponsor will determine when a study will be stopped. The Principal Investigator always has the discretion to initiate stopping the study based on patient safety or if information indicates the study's results are compromised.

JJVC reserves the right to terminate the study at any time for any reason. Additionally, the IEC/IRB reserves the right to terminate the study if an unreasonable risk is determined. The study can be terminated by the Principal Investigator at the individual clinical site due to specific clinical observations, if in their opinion, after a discussion with JJVC, it is determined that it would be unwise to continue at the clinical site.

JJVC (and the IEC/IRB and DMC, if applicable) will evaluate all adverse events. If it is determined that an adverse event presents an unreasonable risk, the investigation, or that part of the investigation presenting the risk, will be terminated as soon as possible.

Should the study be terminated (either prematurely or as scheduled), the Investigator will notify the IEC/IRB and Regulatory Authority as required by local regulatory requirements.

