Signs may include irregular focal infiltrates (> 1 mm); active lesions with raised edges; significant diffuse infiltration; anterior corneal to mid-stromal involvement; erosion with overlying staining; conjunctival and lid edema; anterior chamber reaction (iritis); severe bulbar and limbal redness. Symptoms associated with a presumed infectious ulcer (microbial keratitis) may include pain of rapid onset; severe redness; purulent or mucopurulent discharge; tearing; photophobia. For the purposes of reporting, a corneal ulcer which has *any* of the following characteristics should be considered in this category:
 - 1) central or paracentral location;
 - 2) penetration of Bowman's membrane;
 - 3) infiltrate > 2 mm diameter;
 - 4) associated with iritis \geq grade 2;
 - 5) associated with any increase in intraocular pressure;
 - 6) culture positive for microorganisms;
 - 7) increasing size or severity at subsequent visits.
- b) Any central or paracentral corneal event (such as vascularization) that results in permanent opacification.
- c) Any serious adverse ophthalmic events including hypopyon and hyphema.
- d) Any neovascularization within the central 6 mm of the cornea.
- e) The loss of two or more lines of visual acuity that fail to resolve.

Clinical Study Protocol

Johnson & Johnson Vision Care, Inc.

f) All cases of iritis.

Diagnoses and conditions that are considered Ocular Serious Adverse Events include, but not limited to:

- Microbial Keratitis (MK)
- Iritis (including cells in the anterior chamber)
- Permanent decrease in best spectacle corrected visual acuity equivalent to 2 acuity lines or greater
- Central Corneal Opacity
- Central Corneal Neovascularization
- Uveitis
- Endophthalmitis
- Hypopyon
- Hyphemia
- Penetration of Bowman's Membrane
- Persistent Epithelial Defect
- Limbal cell Damage leading to Conjunctivalization

Significant Adverse Events – are defined as events that are symptomatic and warrant discontinuation (temporary or permanent) of the contact lens wear or require medical treatment to maintain normal ocular health.

Per ISO 11980, significant but non-serious adverse events should include, but not be limited to:

- a) peripheral non-progressive non-infectious ulcers;
- b) all symptomatic corneal infiltrative events;
- c) all cases of corneal staining greater than or equal to grade 3;
- d) a temporary loss of two or more lines of best corrected visual acuity (for greater than or equal to 2 weeks);

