13.4.1. Reporting Adverse Events to Sponsor

Serious/Significant Adverse Events

The Investigator will inform the sponsor of all serious/significant adverse events occurring during the study period as soon as possible by e-mail or telephone, but no later than 24 hours following discovery of the event. The Investigator is obligated to pursue and obtain information requested by the Sponsor in addition to that information reported on the eCRF. All subjects experiencing a serious/significant adverse event must be followed up and all outcomes must be reported.

When medically necessary, the Investigator may break the randomization code to determine the identity of the treatment that the subject received. The Sponsor and study monitor should be notified prior to unmasking the test articles.

In the event of a serious/significant adverse event, the Investigator must:

- Notify the Sponsor immediately.
- Obtain and maintain in the subject’s records all pertinent medical information and medical judgment for colleagues who assisted in the treatment and follow-up of the subject.
- Provide the Sponsor with a complete case history which includes a statement as to whether the event was or was not related to the use of the test article.
- Notify the IEC/IRB as required by the IEC/IRB reporting procedure according to national regulations.

Unanticipated (Serious) Adverse Device Effect (UADE)

In the event of an Unanticipated (Serious) Adverse Device Effect (UADE), the Investigator will submit a report of the UADE to the Sponsor and IEC/IRB as soon as possible, but no later than 24 hours after the Investigator first learns of the effect. This report is in addition to the immediate notification mentioned above.

The Sponsor must conduct an evaluation of the UADE and must report the results of the evaluation to FDA, the IEC/IRB and participating Investigators within 10 working days after the Sponsor first receives notification of the effect.

Clinical Study Protocol

Johnson & Johnson Vision Care, Inc.

Non-Serious Adverse Events

All non-serious adverse events, including non-serious adverse device effects, will be reported to the sponsor by the Investigator no later than 2 days from discovery.

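### After an SAE that may be lens-related, the Synopsis requires dispensing to stop while section 11 makes it optional; handling of corneal infiltrates is also left open

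*Combined protocol and SAP*

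**What the plan says.** **Stopping of dispensing.** The Synopsis (Study Termination) names two triggers: a UADE, and an SAE whose causal link to a test article cannot be excluded. Either one "will result in stopping further dispensing investigational product". It adds that the Sponsor Medical Monitor may unmask and "may discuss this with the Principal Investigator before any further subjects are enrolled", and closes with "See section 11 for additional study-specific stopping rules".

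Section 11 names one or more USADE, or "any SAE where the relationship to study agent cannot be ruled out, may result in stopping" further dispensing of test article. The sponsor may unmask and "will discuss this with the Investigator before any further subjects are enrolled". Section 11 also leaves it to the sponsor to determine when a study is stopped. If an adverse event is judged an unreasonable risk, the investigation or the part concerned "will be terminated as soon as possible".

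**Infiltrates.** Section 8.2 is a list of reasons for which a subject will be withdrawn. One entry is having had a Corneal Infiltrative Event (CIE), with no limit by grade, symptoms or resolution. Step 2.13 (reused at Visits 3 and 4) and step U.9 list corneal infiltrate among significant slit lamp findings. Both withhold lenses for the time being and require follow-up to resolution. Both allow the subject to continue if the investigator thinks it appropriate, and both mention discontinuation as another outcome. Neither refers to 8.2.

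**The concern.** A stopping rule has to be settled before the event that triggers it. As written, a sponsor that goes on dispensing after one possibly related SAE follows section 11 and breaches the Synopsis. A sponsor that stops without speaking to the investigator follows the Synopsis on that step and breaches section 11. The subjects are children aged 7 to 17, and section 16.4 provides no data monitoring committee, so the written rule carries more weight than usual.

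For infiltrates, two sites could each follow a part of the protocol and treat the same finding differently. One would withdraw the child and the other would resume lens wear. Withdrawn subjects are not replaced (sections 4.3 and 8.2), and they leave the per-protocol set, which requires completion of all visits (section 14.3).

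**Working it through.** The main check compares texts. Arithmetic is needed only for the size.

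**1. Synopsis against section 11**

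| Element | Synopsis | Section 11 |
|---|---|---|
| Device-effect trigger | UADE | USADE |
| SAE trigger | link to a test article not excluded | link to study agent not excluded |
| Consequence | *will* stop dispensing | *may* stop dispensing |
| Product covered | investigational product | test article |
| Discussion with investigator before further enrolment | *may* | *will* |

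- *Trigger.* Section 13.2.1 defines a possibly related event as one whose causal relationship cannot be excluded, so the SAE trigger is in substance the same in both texts. As an example, section 13.1 lists "Iritis (including cells in the anterior chamber") as an ocular SAE with no grade limit. One possibly related case must stop dispensing under the Synopsis and need not under section 11.
- *Product.* The Synopsis lists EMO-118 and EMO-114 as investigational and MiSight and 1-Day Acuvue Moist as approved. Table 1 lists all four as test articles. Read literally, the Synopsis stop covers two lenses and the section 11 stop covers four. Section 4.1 appears to use *investigational lenses* for all three study lenses, so the difference may be unintended.
- *Precedence.* No section says which text governs. The Synopsis describes the section 11 rules as additional, yet section 11 restates the same SAE trigger with a weaker consequence.

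**2. Section 8.2 against steps 2.13 and U.9**

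- Withdrawing the subject satisfies all three.
- Continuing after resolution is allowed by 2.13 and U.9. It breaches 8.2 unless CIE is read narrowly enough to leave out the finding.
- The protocol does not settle that reading. Section 13.1 separates symptomatic and significant infiltrative events from non-significant ones (below Grade 2, no symptoms, no medication), and 8.2 does not say which of these CIE covers.

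**3. How often this could arise**

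*Exposure.* Section 6.1 plans about 7 days of run-in and 14 days per study lens: 7 + 3 × 14 = 49 days.

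- 50 completers: 50 × 49 / 365.25 = 6.71 patient-years.
- All 75 enrolled, full wear (upper bound): 75 × 49 / 365.25 = 10.06 patient-years.

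*Infiltrates.* The retrospective cohort in the MiSight package insert (Appendix C) gives 14 / 2134 = 0.656% per year (95% CI 0.36 to 1.10%).

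- Expected events m: 6.71 × 0.00656 = 0.044; 10.06 × 0.00656 = 0.066.
- Chance of at least one, 1 − exp(−m): 4.3% and 6.4%.
- Across the CI: 6.71 × 0.0036 = 0.024 (2.4%) to 10.06 × 0.0110 = 0.111 (10.5%).

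*Cross-check.* In the MiSight randomized trial (same insert), infiltrative keratitis is given for 1 of 130 MiSight eyes and 2.1% of 140 control eyes. The control count extracts as 8, which would be 5.7%; 2.1% × 140 = 2.9, taken as 3.

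- Follow-up: 109 completers × 3 = 327 to 135 dispensed × 3 = 405 patient-years.
- Four eyes, each counted as a subject: 4 / 405 = 0.99% to 4 / 327 = 1.22% per year.
- Expected here: 6.71 × 0.0099 = 0.066 to 10.06 × 0.0122 = 0.123, a 6.4 to 11.6% chance of at least one.
- If the count of 8 were right (9 eyes): 2.2 to 2.8% per year, 0.15 to 0.28 events, a 14 to 24% chance.

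*Serious ocular events.* The documents give no rate for iritis. The MiSight trial reports no serious ocular event over those 327 to 405 patient-years. The cohort has 2 microbial keratitis cases in 2134 patient-years: 6.71 × 2 / 2134 = 0.006 to 10.06 × 2 / 2134 = 0.009 expected here.

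**The case against.** **Nobody is given instructions that cannot be followed.** Stopping all dispensing and discussing the event satisfies both texts, and withdrawing a subject with an infiltrate satisfies 8.2, 2.13 and U.9. This is correct. A reader might infer that compliance is impossible, and the documents do not support that. The defect is that what one text requires, the other leaves optional.

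**Section 11 is the full text and names the sponsor as decision-maker.** That is a reasonable guess at the intent, but no section says it overrides the Synopsis.

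**The infiltrate texts can be read together.** Steps 2.13 and U.9 are generic notes covering several findings, an infiltrate is a slit lamp sign rather than a diagnosed event, and both notes provide for discontinuation. This stands in part. A reader might infer a flat contradiction with 8.2; the supportable point is an undefined term and a missing cross-reference.

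**UADE and USADE.** A reader might infer two different triggers. Section 13.1 already limits a UADE to serious effects, and section 13.4.1 merges the labels as "Unanticipated (Serious) Adverse Device Effect (UADE"). The difference is editorial.

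**Other safeguards exist.** Section 11 requires termination for unreasonable risk. Under section 13.4.1 the investigator reports a UADE within 24 hours, and the sponsor evaluates and reports it within 10 working days. These limit the harm but do not say whether dispensing stops in the meantime.

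**Conclusion.** The concern holds in this form. The Synopsis and section 11 disagree on whether dispensing must stop, which products are covered, and whether discussion with the investigator is required. The infiltrate point is real but secondary.

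The size is small. Less than one infiltrate is expected under every assumption above, and serious ocular events should be rarer still. A reader might infer that the primary comparison is at risk or that iritis would be a frequent trigger; the documents support neither. The effect on the primary analysis is negligible, and the case for change rests on consistent safety handling in children.

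The infiltrate estimates borrow outside rates. The cohort is a chart audit of children fitted at up to 12 years, whereas about half the subjects here are to be 13 to 17. This trial also examines every subject by slit lamp at each visit, and a record audit may miss infiltrates without symptoms. The true rate here could be higher than the central figure. The wording conflict does not depend on any of these rates.

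**What to change.** Reconcile the Synopsis (Study Termination) with section 11 so that four things match: the trigger term, the consequence, the product covered, and the statement on discussion with the investigator before further enrolment. Use the same device-effect label throughout, including in section 13.5.2, which sends a first confirmed amblyopia case to the UADE procedures of section 11.

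Reconcile section 8.2 with steps 2.13 and U.9, add a cross-reference, and state which infiltrative-event classes of section 13.1 the term CIE covers. The sponsor decides which reading stands in each case.

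The cost is wording in the next amendment, IEC/IRB review of the revision (section 18.3), and a note to sites. No design or sample size change is needed.
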